5.1 Sample Size

There are approximately 650 subjects planned for this study. In order to have the desired power for the secondary endpoint of vIGA-AD Success in subjects with a vIGA-AD score of 'Moderate' at randomization, approximately 490 of the subjects to be accrued will have vIGA-AD score of 'Moderate' at randomization. Randomization will be stratified by vIGA-AD score ('Mild' vs. 'Moderate') and by study site.

The sample size of 650 subjects provides approximately 95% power to detect an overall 15% difference (Odds Ratio = 2.1) between treatment groups on vIGA-AD success at Week 4 at α =0.05 using a 2-sided stratified Cochran-Mantel-Haenszel (CMH) test. The results from a recent Phase 2 study (ARQ-151-212) of Roflumilast cream 0.15% compared to vehicle treatment were used to estimate the treatment difference. Specifically, in the Phase 2 trial, approximately 37% of subjects demonstrated vIGA-AD Success at Week 4 in the ARQ-151 0.15% group compared to 22% in the vehicle group. The sample size of 490 also provides approximately 90% power to detect an overall 17% difference (Odds Ratio = 2.1) between treatment groups (28% of vIGA-AD Success at Week 4 in vehicle treatment) on vIGA-AD Success at Week 4 among subjects with vIGA-AD score 'moderate' at randomization. The same testing method, the stratified CMH test, will be used as for the primary endpoint.

To control for familywise type I error at level of 0.05, the secondary endpoint of vIGA-AD Success at Week 4 in subjects with vIGA-AD of 'Moderate' at randomization will only be tested if the primary endpoint demonstrates statistical significance. In addition, the remaining secondary endpoints will be inferentially tested only if the primary and secondary endpoint (vIGA-AD Success at Week 4 for subjects with vIGA-AD score of 'Moderate' at randomization) comparisons are statistically significant using the hierarchical testing procedure by partitioning of alpha (see Section 6.5 for more details).

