6.2.1 Multiple Imputation

For the primary efficacy endpoint of vIGA-AD success at Week 4 and the secondary endpoint of vIGA-AD success at Week 4 among subjects with a 'Moderate' randomized vIGA-AD score, the primary analysis will impute missing values using a Predictive Mean Matching (PMM) sequential-regression multiple imputation model for the ITT population. This is a three-step process.

1. The first step is to understand the pattern of missingness. In order to perform the multiple imputation, a monotone missing pattern has to be achieved. For example, if there exist values for baseline and Week 4 visits, but missing values for the Week 1 or 2 visits, the Markov-Chain Monte-Carlo (MCMC) method will be used to impute the small amount of missing data that may be missing at the intermediate visits that is required to make the missing data pattern monotone before applying the multiple imputation algorithm. This method uses a non-informative Jeffreys prior to derive the posterior mode from the expectation-maximization (EM) algorithm as the starting values for the MCMC method. The MCMC method will use the seed 6457149. The vIGA-AD score will be treated as a continuous variable for this step and the model will include the vIGA-AD scores at baseline, Week 1, Week 2, and Week 4. To avoid values that could not be observed in practice, imputed values will be rounded to the nearest integer (Round=1 option in PROC MI) in the range of 0 to 4.

To determine the number of multiply-imputed datasets to be created at this step, the proportion of datapoints with non-monotone pattern across all visits and subjects will first be derived as follows:

	STATISTICAL ANALYSIS PLAN, Version 1.0
Protocol Number: ARQ-151-312	Sponsor: Arcutis Biotherapeutics, Inc.

 $\frac{number\ of\ non\ monotone\ visits\ accross\ all\ visits\ and\ subjects}{total\ number\ of\ expected\ visits\ across\ all\ subjects}*100$

Then, the following table will be used:

Non-monotone	Number of
Missing Data	Imputed Datasets
≤ 2%	1
$> 2\%$ to $\le 5\%$	3
> 5%	10

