- 2. Once the monotone pattern is achieved, the next step is to implement the imputation algorithm. For this, the PMM regression method will be used. This method is particularly helpful if the normality assumption is violated. For subjects with complete data up to a particular visit, a PMM regression model will be fit that includes the outcome at that visit as the dependent variable and as independent variables, the treatment group, pooled study site, and vIGA-AD score outcomes at previous visits, using a seed of 482371. For other scales/questionnaires, the actual baseline vIGA score will also be included as an independent variable. This process will be repeated 25 times, resulting in a total of 25 to 250 complete analysis datasets, depending on the number of imputed monotone datasets that are required. The seed may be changed after unblinding in case of any issues with the imputation process, and it will be documented in the CSR if any change is required.
- 3. For each completed dataset, compute the necessary derived variables. The dichotomous success rate (clear or almost clear with at least a 2-point change from baseline) will be derived. For each of the 25 to 250 complete analysis datasets, the results will be analyzed using a CMH analysis, adjusted for the pooled study site and randomized vIGA-AD score for the primary efficacy endpoint and adjusted for the pooled site for the secondary efficacy endpoint. Results will be combined into one multiple imputation inference as follows:
 - a. Common proportion of success, common Mantel-Haenszel (MH) proportion difference (and associated 95% CI), and common MH odds ratio (and associated common 95% CI) will be combined using PROC MIANALYZE based on Rubin's rule. Common MH odds ratios and associated common 95% CI will first be normalized using a log-transformation before being combined using PROC MIANALYZE. The resulting combined common MH odds ratio and associated combined common 95% CI will be back-transformed to the arithmetic scale before being presented in a table.

	STATISTICAL ANALYSIS PLAN, Version 1.0
Protocol Number: ARQ-151-312	Sponsor: Arcutis Biotherapeutics, Inc.

- b. For the combined common proportion of success, the associated combined common 95% CI will be calculated as per Lott and Reiter multiple imputation Wilson interval method¹.
- c. Two p-values will be produced for each analysis:

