 - i. The primary p-value will be obtained from a multiple imputation CMH test, where CMH general association statistics and their standard errors obtained from the analysis of each multiply-imputed dataset will be transformed as per Wilson-Hilferty² before being combined using PROC MIANALYZE based on Rubin's rule. Because the Wilson-Hilferty transformation is a monotone transformation, the p-value for the CMH test is the one-sided p-value from the t distribution. This p-value will be the primary p-value used to evaluate the result according to the multiple testing strategy described in Section 6.5.
 - i. Should the common MH odds ratio from the analysis of at least one of the multiply-imputed datasets be not estimable, combined common MH odds ratio and associated combined common 95% CI and p-value will not be presented. Under such circumstance, conclusions will be based on the p-value obtained from a multiple imputation test of the proportion difference, where the common proportion difference using MH weights and associated common standard errors based on the Sato variance estimator obtained from the analysis of each multiply-imputed dataset will be combined using PROC MIANALYZE based on Rubin's rule.

Similar multiple imputation method will be used for the average weekly WI-NRS and EASI total score.

For the average weekly WI-NRS, it's the missing average weekly WI-NRS data (i.e., those that cannot be computed because only 3 or less non-missing assessments are available during a given week) at Weeks 1, 2, 3, and 4 that will be multiply imputed, not the missing daily WI-NRS data. Since the missing average weekly WI-NRS values have a precision of 1 decimal place, the MCMC imputation for the non-monotone missing data will be restricted to values between 0 and 10, rounded to the 1st decimal (i.e., 0.1). Imputation of missing data for WI-NRS will be based on the ITT population, i.e., all randomized subjects will be included in the imputation process.

For the EASI total score, it's the missing EASI total score data at Weeks 1, 2, and 4 that will be imputed, not the missing EASI question score data. Since the missing EASI total scores have a precision of 1 decimal place, the MCMC imputation for the non-monotone missing data will be

	STATISTICAL ANALYSIS PLAN, Version 1.0
Protocol Number: ARQ-151-312	Sponsor: Arcutis Biotherapeutics, Inc.

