6.4 Multicenter Studies

The study will be conducted at approximately 60 study sites in the US, Canada, and Poland. During the conduct of the study, additional countries and/or sites may be added if necessary.

Sites with less than 16 subjects in the ITT population will be pooled within a country:

- a. Sites with less than 16 subjects will be ordered from lowest to highest in terms of number of ITT subjects. In case of ties, the ordering for tied sites will be determined according to the site identification number (from smallest to largest).
- b. Sites will be combined beginning at the smallest until the resulting pooled site contains at least 16 ITT subjects with at least 1 subject in each treatment group. The sites pooled in this way will be considered as a single site in the statistical analyses.
- c. The process described above will resume for the remaining sites not meeting the criterion of at least 16 ITT subjects with at least 1 subject in each treatment group. If the final set of pooled sites does not meet the criterion of at least 16 ITT subjects with at least 1 subject in each treatment group, the final set will be pooled with the preceding pooled site.
- d. If there is only one site with less than 16 ITT subjects with at least 1 subject in each treatment group, then this site will be combined with the site with the second lowest number of subjects. As above, in the case of ties, the ordering for tied sites will be determined according to the site identification number (from smallest to largest).

As a sensitivity analysis of different pooling strategy, sites that have randomized less than 50% of the number of randomized subjects at the site with the largest number of randomized subjects, those sites will be pooled within each country. The sensitivity analysis of pooling strategy will be applied for the primary endpoint only.

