6.5 Multiple Comparisons/Multiplicity

To control for familywise type I error at level of 0.05, the secondary endpoint of vIGA-AD Success at Week 4 for subjects with vIGA-AD score of 'Moderate' at randomization will only be tested if the primary endpoint demonstrates statistical significance. In addition, the remaining secondary endpoints will be inferentially tested only if the primary and the secondary endpoint (vIGA-AD Success at Week 4 for subjects with vIGA-AD score of 'Moderate' at randomization) comparisons are statistically significant using hierarchical testing procedure by partitioning of alpha.

Upon successful demonstration of statistical significance for the primary and above secondary endpoint, the remaining endpoints will be grouped into secondary endpoint family 1, comprised of the 4-point reduction on the WI-NRS at Week 4, Week 2 and Week 1, and secondary endpoint family 2, comprised of the EASI-75 at Week 4, vIGA-AD of 'clear' or 'almost clear' at Week 4,

	STATISTICAL ANALYSIS PLAN, Version 1.0
Protocol Number: ARQ-151-312	Sponsor: Arcutis Biotherapeutics, Inc.

vIGA-AD of success at Week 2 and Week 1, vIGA-AD of 'clear' or 'almost clear' at Week 2 and Week 1. An alpha level of 0.03 will be used to test the endpoints in the secondary endpoint family 1 sequentially. An alpha level of 0.02 will be used to test the endpoints in secondary endpoint family 2 sequentially.

In addition to the partitioning of the overall 0.05 alpha into two families, the Fallback Method will be applied. The fallback method is a modification of the fixed-sequence method, providing opportunity to test an endpoint later in the sequence even if an endpoint tested early in the sequence has failed to show statistical significance. The order of the endpoints remains important. The appeal of the fallback method is that if an endpoint later in the sequence has a robust treatment effect while the preceding endpoint is unsuccessful, there is a modest amount of alpha retained as a fallback to allow interpretation of that endpoint without inflating the Type I error rate. Applying the fallback method begins by dividing the total alpha (not necessarily equally) among the endpoints and maintains a fixed sequence for the testing. In this study, the Fallback Method will be applied to the fixed sequence of testing Family 1, and then Family 2.

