As the testing sequence progresses, a successful test preserves its assigned alpha as "saved" ("unused" or "accumulated") alpha that is passed along to the next test in the sequence, as is the case for the sequential method. This accumulated alpha is added to the prospectively assigned alpha (if any) of that next endpoint and the summed alpha is used for testing that endpoint. Thus, as sequential tests are successful, the alpha accumulates for the endpoints later in the sequence; these endpoints are then tested with progressively larger alphas.

[figure not shown]
In this study, the Fallback Method will be applied following this sequence:

Family 1: Testing will proceed at the 0.03 level sequentially within Family 1. Should all 3 endpoints in Family 1 be statistically significant at the 0.03 level, then the full 0.03 alpha will be carried to Family 2. Family 2 would then be tested at the full (α =0.02+0.03=0.05).

Should, anywhere during the sequential testing of Family 1, there is a p-value >0.03, the testing within Family 1 will stop, and no additional alpha can be carried over to Family 2.

	STATISTICAL ANALYSIS PLAN, Version 1.0
Protocol Number: ARQ-151-312	Sponsor: Arcutis Biotherapeutics, Inc.

Figure 2 Multiple Testing Scheme

Achievement of vIGA-AD success is a score of "clear" or "almost clear" plus a 2-grade improvement from baseline.

WI-WRS Success is a 4-point reduction in WI-NRS among subjects ≥12 years old with WI-NRS ≥ 4 at baseline.

EASI-75: achievement of at least a 75% reduction in the Eczema Area and Severity Index

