12.1.3 Primary Endpoint Analysis

For the primary analysis, missing vIGA-AD scores will be imputed using multiple imputation as described in Section 6.2.1. These imputations will result in a minimum of 25 to a maximum of 250 complete analysis datasets, depending on the number of imputed monotone datasets that are required.

Percentages of subjects having a vIGA-AD Success (refer to Section 12.1.1) will be presented by visit and treatment group based on multiply imputed data in the ITT population along with a 95% Wilson CI. The common MH odds ratio and common MH proportion difference, adjusted for the randomization factors (i.e., randomized vIGA-AD score and pooled study site) will also be provided along with their common associated 95% CIs. Additionally, count and percentage of subjects having a vIGA-AD success, count and percentage of subjects in each category of the vIGA-AD scale, and descriptive statistics for the vIGA-AD scores, change in vIGA-AD score from baseline and percent change in vIGA-AD score from baseline will be presented by visit and treatment group based on observed data in the ITT population.

The primary endpoint (vIGA-AD Success at Week 4) will then be analyzed using multiple imputation CMH test stratified by the randomization factors. To do so, a CMH analysis will be performed separately for each of the complete multiply imputed analysis data sets, and results will be combined into one multiple imputation inference using the methodology described in Section 6.2.1. Statistical significance will be concluded at the 5% significance level (2-sided). Should the odds ratio be not estimable for at least one multiply imputed dataset, the conclusion of the study will be based on the p-value obtained from a MH test, stratified by the randomization factors, for the common MH proportion difference at Week 4.

The following sensitivity analyses to the primary analysis of the primary endpoint will be performed:

	STATISTICAL ANALYSIS PLAN, Version 1.0
Protocol Number: ARQ-151-312	Sponsor: Arcutis Biotherapeutics, Inc.

- Multiply-imputed data (refer to Section 6.2.1) on mITT population (refer to Section 4.2) and
- Tipping Point analysis (refer to Section 6.2.3) on ITT population.
- Non-responder imputation (refer to Section 6.2.2) on ITT population.
- Observed data on ITT population (refer to Section 4.1).
- Observed data on PP population (refer to Section 4.3).

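### When the MH odds ratio is not estimable in even one imputed dataset, the SAP replaces the CMH p-value with a risk-difference p-value that is anti-conservative at 2:1 allocation if vehicle has no successes; very sparse secondary endpoints are exposed, the primary in practice is not

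*SAP*

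**What the plan says.** SAP 6.2.1, step 3c, names the multiple-imputation CMH p-value (combined after a Wilson-Hilferty transformation) as the one that enters the testing strategy of 6.5. It then provides for the case where the common MH odds ratio cannot be estimated in at least one of the 25 to 250 imputed datasets: "Under such circumstance, conclusions will be based on the p-value obtained from a multiple imputation test of the proportion difference". That test uses MH weights and the Sato variance.

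SAP 12.1.3 repeats the rule for the primary endpoint: "Should the odds ratio be not estimable for at least one multiply imputed dataset, the conclusion of the study will be based on the" p-value of an MH test of the common proportion difference. SAP 12.2 analyses the secondary endpoints in the same way, so the rule also governs Family 1 (WI-NRS at Weeks 4, 2 and 1; alpha 0.03) and Family 2 (EASI-75 and the vIGA-AD endpoints; alpha 0.02, or 0.05 if all of Family 1 passes). SAP 12.3 has the same fallback for exploratory endpoints, with nominal p-values only.

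SAP 6.5 introduces the testing order with the aim "To control for familywise type I error at level of 0.05".

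**The concern.** A failure to estimate an effect measure should not change the test. The CMH statistic compares observed with expected successes within strata. It can be computed with no vehicle successes, as long as at least one success falls in a stratum that holds both arms and is not all successes.

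Under this rule the observed data decide which test applies, and they do so where the two tests disagree most. The replacement test estimates its variance from the observed successes. With none on vehicle, the smaller arm adds almost nothing to that estimate, although under the null it carries about two thirds of the true variance. A single imputed dataset out of 25 or more is enough to trigger the switch.

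At stake is the size of the test for sparse, alpha-controlled secondary endpoints, and through them the familywise claim. Week 1 WI-NRS matters further because it is the last test before alpha is released: "Should all 3 endpoints in Family 1 be statistically significant at the 0.03 level", Family 2 is tested at 0.05.

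**Working it through.** **Inputs.** N=650 and 2:1 allocation (SAP 5.1, 3.4), so n1=433 active and n0=217 vehicle. Vehicle Week 4 success is 22% overall and 28% in the Moderate subset of 490, about 163 on vehicle (SAP 5.1). The documents give no Week 1, Week 2 or WI-NRS rates, no WI-NRS population size and no missing-data rate; these are assumed below. They give no figure for the size of this rule, so there is none to reproduce.

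**Step 1: one stratum, a active and c vehicle successes, t=a+c.**

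- Risk difference: d = a/n1 − c/n0. Sato variance = (d·P + Q)/w², with w = n1·n0/N, P = [n1²c − n0²a + n1·n0(n0 − n1)/2]/N², Q = [a(n0 − c) + c(n1 − a)]/(2N).
- CMH: X² = (a − t·n1/N)² / [t(N − t)·n1·n0/(N²(N − 1))].

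For 4 v 0: d = 4/433 = 0.00924, SE = 0.00460, z = 2.01, p = 0.045. CMH: expected 4×433/650 = 2.665, variance 0.885, X² = 1.335²/0.885 = 2.01, p = 0.156.

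For 6 v 0: p = 0.014 against CMH 0.082.

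The reason is visible in the variances. With c=0 the Sato variance is close to a/n1², while the variance under equal rates is close to a/(n1·n0). Their ratio is n0/n1, about one half, so z is about √a instead of √(a/2). At 1:1 the tests agree (325 per arm, 4 v 0: 0.044 and 0.045). Active successes needed against zero on vehicle: 4 instead of 8 at 0.05, and 6 instead of 11 at 0.02.

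**Step 2: exact size.** All binomial outcomes are enumerated under equal rates, with one stratum and complete data. The odds ratio is pooled on the log scale (step 3a), so a zero in either arm is taken to trigger the switch. A zero in the active arm makes the replacement conservative (0 v 2: 0.155 against CMH 0.046).

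| True rate, both arms | Switch / CMH at 0.05 | Switch / CMH at 0.02 |
|---|---|---|
| 0.25% | 0.016 / 0.036 | – |
| 0.5% | 0.069 / 0.042 | 0.009 / 0.013 |
| 0.75% | 0.100 / 0.039 | – |
| 1% | 0.098 / 0.041 | 0.039 / 0.014 |
| 1.25% | 0.082 / 0.044 | 0.041 / 0.014 |
| 2% | 0.053 / 0.048 | 0.025 / 0.018 |
| 2.5% | 0.050 / 0.050 | 0.020 / 0.018 |

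For WI-NRS at nominal 0.03 with assumed populations of 200 to 325, the peak is 0.063 to 0.065 at rates of 3.2% (133/67) down to 2.0% (217/108), against CMH 0.020-0.023.

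**Step 3: strata.** SAP 6.4 pools until "the resulting pooled site contains at least 16 ITT subjects with at least 1 subject in each treatment group". That guarantees both arms per pooled site, not per site-by-severity stratum. Simulating 60 sites pooled by this rule (blocks of 6 assumed) gives, at nominal 0.05, 0.050/0.032 at a 0.5% rate, 0.088/0.041 at 1% and 0.054/0.050 at 2%. CMH has zero variance in 0.16% of trials with a success at 0.5%, and in 0.02% at 1%.

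**Step 4: imputation** (1% rate, nominal 0.05, 25 imputations). If donors come from both arms alike, size is 0.071 with 5% missing and 0.045 with 10%, so the excess disappears. The SAP's regression, however, takes "as independent variables, the treatment group, pooled study site, and vIGA-AD score outcomes at previous visits". Imitating it with 5 nearest donors (assumed) draws about 92% of donors from the subject's own arm and gives 0.097 and 0.087. The preliminary step for intermittent gaps has no treatment term ("the model will include the vIGA-AD scores at baseline, Week 1, Week 2, and Week 4"); 5% intermittent missingness alone gives 0.091. CMH stays at 0.044-0.050 in the imitations of the SAP's model.

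**Step 5: exposure.** Chance of no vehicle success: primary 0.78^217 = 3.8e-24; Moderate 0.72^163 = 5.6e-24. With 217 on vehicle, a 1% rate gives 0.99^217 = 0.11 and a 2% rate gives 0.98^217 = 0.012.

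**Step 6: familywise illustration.** Take a null, non-sparse Family 1 endpoint (size 0.03) and a null, sparse Family 2 endpoint at nominal 0.02 (size 0.041). Assume that the other gates pass and treat the families as independent: 0.03 + 0.97×0.041 = 0.070. With CMH kept: 0.03 + 0.97×0.014 = 0.044.

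**The case against.** The best defence is that the rule is fixed in advance and keeps test and estimate together. SAP 12.1.1 makes the odds ratio the primary summary with the proportion difference as support, and 12.3 treats CMH as the test belonging to the odds ratio. When the ratio does not exist, moving to the difference is coherent. The exposed endpoints are also likely to stand late in the sequence, the band of rates is narrow, the rule is conservative at 0.25%, and with 10% missing and pooled donors the excess vanishes.

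The points on rarity stand, and they set the weight of this point. The alignment argument does not rescue the rule. Pre-specification does not correct a test that can reject at about twice its nominal level, and the difference can be reported without deciding on it.

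A reader might infer more than the documents support:

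- **That the trial's main conclusion is at risk,** because 12.1.3 writes the rule for the primary endpoint. At the planning rates the trigger is practically impossible.
- **That only Week 1 endpoints are exposed.** Week 1 is the most plausible place, but the rule is limited to no visit and the documents give no Week 2 or WI-NRS rates.
- **That a definite familywise rate follows.** It depends on the chance that earlier tests pass and on how many endpoints are null, which the documents do not settle. Nor must Family 1 pass before the 0.05 claim can fail, because the two families' alphas add (Step 6).

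**Conclusion.** The point holds as a minor defect. The switch is unnecessary, and with no vehicle successes at 2:1 it is anti-conservative. Size peaks at about 0.10 at nominal 0.05, about 0.065 at 0.03 in an assumed smaller WI-NRS population, and about 0.04 at 0.02. CMH stays below nominal at each of these peaks.

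An alpha-controlled endpoint is exposed if its success rate is below about 2% with 217 vehicle subjects, or somewhat higher in a smaller WI-NRS population. Whether any endpoint is that sparse is an assumption. The peak sizes are for one stratum with complete data and a trigger on a zero in either arm. Stratification lowers the 1% figure at nominal 0.05 from 0.098 to 0.088, and the effect of imputation depends on the missing-data rate and on how donors are chosen. The familywise figure of about 0.07 is an illustration under stated conditions, not an estimate for this trial. Exploratory and subgroup p-values lie outside the familywise claim.

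**What to change.** In SAP 6.2.1 (step 3c) and 12.1.3, and in 12.3 for consistency:

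- Keep the CMH p-value as the decision p-value whether or not the odds ratio is estimable; in 6.2.1 and 12.1.3 this is the multiple-imputation CMH p-value.
- Where the odds ratio is not estimable, report it as such, and give the MH risk difference with its confidence interval as description only.
- State that the CMH statistic is set to 0 in any imputed dataset where its variance is zero (no success in either arm, or successes only in one-arm or all-success strata).

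The cost is SAP wording. No data or design change is needed, and the primary result is untouched. The downside is that the p-value of a sparse secondary endpoint may become less favourable.

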3 STUDY DESIGN

3.1 Overall Design

[figure not shown]
This is a Phase 3, parallel group, double blind, vehicle-controlled study in which Roflumilast cream 0.15% or vehicle is applied QD x 4 weeks to subjects with mild to moderate atopic dermatitis.

- Upon determination of eligibility, subjects will be randomized 2:1 to either Roflumilast cream 0.15% or matching vehicle cream. The randomization will be stratified by vIGA-AD score at baseline ('Mild' vs. 'Moderate') and by study site.
- At the Week 4 visit, subjects may be eligible to enroll in an open label extension study (ARQ-151-313) in which they will receive Roflumilast cream 0.15% QD.

The trial design is represented schematically in Figure 1.

	STATISTICAL ANALYSIS PLAN, Version 1.0
Protocol Number: ARQ-151-312	Sponsor: Arcutis Biotherapeutics, Inc.

Figure 1 Study Schema

A Phase 3, 4-Week, Parallel Group, Double Blind, Vehicle-Controlled Study of the Safety and Efficacy of ARQ-151 Cream 0.15% Administered QD in Subjects with Atopic Dermatitis

Approximately 650 subjects with atopic dermatitis will be randomized 2:1 to receive either:

• Roflumilast cream 0.15% or Vehicle cream

Subjects will have ≥3% BSA involvement (excluding the scalp, palms, soles) with a vIGA-AD score of '2' (mild) or '3' (moderate) for study entry

Up to 50% of the subjects will be \geq 18 years old

	STATISTICAL ANALYSIS PLAN, Version 1.0
Protocol Number: ARQ-151-312	Sponsor: Arcutis Biotherapeutics, Inc.

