4.6 WI-NRS Population

WI-NRS population will be a subset of the ITT population among subjects ≥ 12 years old with average weekly baseline WI-NRS score ≥ 4 .

The subjects in WI-NRS population are those:

- 1. Completed at least 4 of 7 evaluable daily WI-NRS questionnaires during the last 7 days of the Screening period;
- 2. Have a mean baseline WI-NRS score ≥ 4.0, defined as the average of all non-missing scores reported during the last 7 days of the Screening period if at least 4 of 7 evaluable daily WINRS questionnaires available. If 4 or more evaluable daily questionnaires are missing, then the data will be treated as missing.

All subjects will be analyzed according to the treatment group and stratum to which they were randomized.

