5.7 Statistical Tests

Unless otherwise specified, all statistical tests will be two-sided and will be performed with a significant level of 0.05. Confidence intervals (CIs) will be two-sided with 95% coverage.

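### SAP 6.2.1 imputes weekly itch averages with no age term and ignores a week's 1–3 recorded scores; the demonstrated cost is avoidable imputation noise

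*SAP*

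**What the plan says.** - **Who is tested.** SAP 4.6: "WI-NRS population will be a subset of the ITT population among subjects" aged 12 or older whose average weekly baseline WI-NRS is at least 4.
- **Who is imputed from.** SAP 6.2.1: "Imputation of missing data for WI-NRS will be based on the ITT population, i.e., all randomized subjects will be included in the imputation process". Randomization is open from age 6 (Protocol 4.5.1), so ages 6–11 are included.
- **What counts as missing.** Weekly averages are imputed rather than daily scores. The missing ones are "those that cannot be computed because only 3 or less non-missing assessments are available during a given week". A week with one, two or three scores is handled like an empty week.
- **The model.** Step 2 of SAP 6.2.1 uses predictive mean matching (PMM) on treatment, pooled site and outcomes at earlier visits. It adds: "For other scales/questionnaires, the actual baseline vIGA score will also be included as an independent variable". Neither age nor any score from the week being imputed is listed. Step 1 fills intermittent gaps by MCMC, also on all randomized subjects.
- **The test.** SAP 6.5: "An alpha level of 0.03 will be used to test the endpoints in the secondary endpoint family 1 sequentially", in the order Week 4, Week 2, Week 1. SAP 5.7: "Unless otherwise specified, all statistical tests will be two-sided and will be performed with a significant level of 0.05".
- **Sensitivity analyses.** SAP 12.2 plans non-responder and observed-data analyses for itch, only if the hierarchy permits. The tipping-point analysis in SAP 6.2.3 covers vIGA-AD success only.

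**The concern.** Two pieces of available information are left out of the imputation.

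First, a subject's own scores from the target week say more about that week's mean than earlier weeks do, yet they are set aside whenever fewer than four exist. No planned responder analysis recovers them: non-responder imputation scores such a week as a failure, and the observed-data analysis drops it.

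Second, the itch endpoints exclude ages 6–11, but those children help to fit the model and can be matching donors. Without an age term, the model assumes that they follow the same itch course as older subjects, given treatment and history.

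The three itch tests gate one another at 0.03. One p-value above 0.03 ends Family 1 and leaves Family 2 at 0.02 instead of 0.05 (SAP 6.5). Noise that is cheap to remove from a gatekeeper is worth removing.

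**Working it through.** **1. The plan's own figure.** The documents give no responder rate, power or missing-data share for itch. The nearest figure is SAP 5.1: "The sample size of 650 subjects provides approximately 95% power to detect an overall 15% difference (Odds Ratio = 2.1) between treatment groups". With 37% versus 22%, 2:1 allocation and two-sided 0.05:
- group sizes 433.3 and 216.7; pooled rate (2×0.37 + 0.22)/3 = 0.32
- SE under the null = √[0.32×0.68×(1/433.3 + 1/216.7)] = 0.0388
- SE under the alternative = √[0.37×0.63/433.3 + 0.22×0.78/216.7] = 0.0365
- power = Φ[(0.15 − 1.96×0.0388)/0.0365] ≈ 97.9%

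The stated 95% is conservative (95.6% if 15% are lost, an assumption). It has no bearing on itch.

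**2. Can partial weeks occur?** The Week 4 average uses days 22–28 (SAP Table 4). The visit may fall on day 29 − 3 = 26 (SAP Table 1). If the diary ends at that visit, four or five diary days remain. That still meets the four-day minimum, but one or two missed entries leave three. How often this happens is unknown.

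**3. Wrong responder status.** Simulated trials had 651 subjects, 2:1, daily integer scores 0–10, autocorrelated weeks and PMM with five donors. In 8% of subjects the Week 4 average had only 1–3 diaries. Imputed 4-point status was compared with the true seven-day status in subjects aged 12 and over with baseline of at least 4. Assumed: 30–45% aged 6–11, daily SD 1.0–1.5, week-to-week correlation 0.70–0.95. Examples at 45% children with the same itch course in both age groups:

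| Daily SD | Correlation | As in SAP | Donors 12+ only | Own scores used |
|---|---|---|---|---|
| 1.0 | 0.95 | 11.7% | 11.6% | 7.7% |
| 1.5 | 0.70 | 22.2% | 22.4% | 13.0% |
| 1.5 | 0.85 | 17.3% | 17.4% | 11.1% |
| 1.5 | 0.95 | 12.7% | 13.4% | 9.7% |

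Over all 16 scenarios the ranges were about 12–22% (SAP) and 7–13% (own scores used), and the SAP method was worse in every one. In the first two rows the gain is 24.4×(0.117 − 0.077) = 1.0 and 24.7×(0.222 − 0.130) = 2.3 fewer wrong statuses per imputed dataset. Over all scenarios it is about 1–4, out of 24–31 imputed subjects.

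**4. Effect on the test.** Assumed: daily SD 1.2, correlation 0.85, 45% children, 150 trials, eight imputations.

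| Week 4 averages affected | SE, SAP | SE, own scores used | Ratio |
|---|---|---|---|
| 3% | 0.0361 | 0.0359 | 1.006 |
| 8% | 0.0368 | 0.0364 | 1.011 |
| 15% | 0.0382 | 0.0375 | 1.019 |

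Simulated rejection rates at 0.03 did not separate the methods (55.3% versus 54.7% at 8%; 48.7% versus 49.3% at 15%). As a guide, suppose power is 80% with own scores used (an assumption). The standardized effect is then 2.170 + 0.842 = 3.012. Dividing by 1.011 or 1.019 gives power Φ(0.81) ≈ 79.1% or Φ(0.79) ≈ 78.4%, a loss of about 1 to 1.6 points.

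**5. Child donors.** Children were 30–46% of donors drawn. With the same itch course, limiting donors to 12 and over gained nothing (see table). Next, children's Week 4 scores were set to differ given history (45% children, SD 1.0, correlation 0.85). The responder rate among imputed subjects moved by −5.7 points (children 1 point higher) to +8.8 points (1 point lower). At 8% imputed, that is 0.08×(−5.7) = −0.5 to 0.08×8.8 = +0.7 points on an arm's rate, in the same direction in both arms.

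**6. Type I error.** With no treatment effect and 8% affected, rejection at 0.03 was 1.6% in 250 trials under both methods (2.8% with complete data). The Monte Carlo SE is √(0.03×0.97/250) = 1.1 points, so small differences cannot be excluded.

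Not modelled: pooled site, baseline vIGA-AD, CMH stratification, and missingness that depends on the week's itch.

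**The case against.** The case for the plan is substantial. Multiple imputation aims at valid group inference, not at recovering each subject's status, and Rubin's rules carry the extra uncertainty into the test. The four-of-seven rule is pre-specified and applied alike at baseline and follow-up. Imputing from all randomized subjects is explicit and keeps the donor pool large. With sites pooled to at least 16 subjects, pooled site can have up to about 650/16 ≈ 40 levels, and dropping ages 6–11 would thin those cells. This stands: the diary loss costs efficiency without invalidating the test, and restricting donors is a trade-off, not a clear gain.

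The planned sensitivity analyses do not answer the point, since neither uses the 1–3 scores and both depend on the hierarchy.

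A reader might go further and infer that child donors bias the itch tests. The documents do not support that. The harm needs a different itch course in children after conditioning on treatment and earlier scores, and no such data are given. Parental help with the scale is no evidence either: footnote e of SAP Table 1 extends it to adolescents, who are in the analysed group. Nor are all imputed values copied from donors, because MCMC fills the intermittent gaps.

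**Conclusion.** The point holds as an avoidable loss of information. Ignoring a week's 1–3 recorded scores makes imputed Week 4 status wrong in about 12–22% of affected subjects rather than 7–13%. It enlarges the SE by about 1–2% if 8–15% of Week 4 averages are affected. The affected share, the daily variability and the proportion aged 6–11 are all assumptions. On age, SAP 3.1 says only "Up to 50% of the subjects will be" 18 or older, so half or more are 6–17, with no split at 12.

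The missing age term is a robustness gap, not a demonstrated bias. It would also be wrong to conclude that the itch tests exceed their alpha: no inflation was seen, within the precision of 250 trials and with missingness unrelated to itch. This is an inexpensive improvement to the plan; the planned analysis is not invalid without it.

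**What to change.** 1. In SAP 6.2.1, add age group (6–11 versus 12 and over) as a predictor in steps 1 and 2 of the WI-NRS imputation, keeping all randomized subjects.
2. In SAP 12.2, add a pre-specified sensitivity analysis of the three Family 1 endpoints, not conditional on the hierarchy, that uses the recorded scores in weeks with 1–3 diaries. Either average all available diaries in the week, or impute the missing days and then average.

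The partial-week mean should not simply be entered as a predictor in the existing model. For donors with complete weeks it equals the outcome, and for subjects with no diaries it does not exist.

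Averaging available days is simple but noisy. A k-day mean differs from the seven-day mean with SD σ√(1/k − 1/7), if days vary independently around the week's mean. At an assumed σ = 1.2 this is 1.11, 0.72 and 0.52 points for one, two and three days. It therefore suits a sensitivity analysis rather than a replacement for the main one.

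Cost: SAP wording, modest extra programming and one additional output, settled before unblinding.
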